11.4. Annual Progress Reports (APRs)

The CI will prepare the APR in accordance with JREOSOP0043. Following review by the sponsor the report will be sent to the REC. The APR is due for submission annually within 30 days of the

anniversary date on which the Ethics committee gave the favourable opinion, until the trial is declared ended.

12. Data management and quality assurance

12.1. Confidentiality

All data will be handled in accordance with the Data Protection Act 1998.

CRFs will not bear the participant's name or other directly identifiable data. The participant's trial ID only, will be used for identification. The sponsor Subject ID log JREOLOG0002 can be used to cross reference participant's identifiable information.

12.2. Data collection tool

The CI will design CRFs, either on paper or online on a secure RedCap database. For paper CRFs, all data will be entered legibly in black ink with a ball-point pen. If the Investigator makes an error, it will be crossed through with a single line in such a way to ensure that the original entry can still be read. The correct entry will then be clearly inserted. The amendment will be initialled and dated by the person making the correction immediately. Overwriting or use of correction fluid will not be permitted.

It is the Investigator's responsibility to ensure the accuracy of all data entered and recorded in the CRFs. The Staff Delegation of Responsibilities Log JREOLOG0004 will identify all trial personnel responsible for data collection, entry, handling and managing the database.

Following receipt of informed consent, maternal demographics and medical history will be collected at delivery. CRFs will be designed for the collection of relevant information. Priority will be given to the collection of key exclusion data: gestation at birth, receipt of IAP (yes/no), type of IAP (list), time between first administration of IAP and delivery (in hours), recent blood transfusion (in last 1 month), in addition to collection of other routine data.

12.3. Incidental Findings

N/A

12.4. Data handling and analysis

A secure password-protected database will be designed and set up using REDCap and will be used by the study sites for entering data. Data from CRFs will be reviewed and corrected in the database by the site study team referring to the original documentation.

12.5. Personal information data flow

Women who agree to participate in this trial will be identified and consented as per the procedures above. Once recruited, a CRF form will be created as above and stored in a locked cabinet. Samples taken will be identified with a unique number that is linked to a participant's CRF. Samples sent to the laboratory at each site will therefore not contain any patient identifiable data. The samples will be stored in a -20°C to -80°C freezer in a locked research laboratory with access restricted to research staff.

13. Archiving arrangements

The trial essential documents along with the trial database will be archived in accordance with the sponsor SOP JREOSOP0016. The agreed archiving period for this trial will be 5 years. Each PI at any participating site will archive the trial essential documents generated at the site for the agreed archiving period in accordance with the signed Clinical Trial Site agreement.

14. Statistical design

14.1. Statistical input in trial design

Statistical design has been discussed with [name], Senior Statistician at Public Health England.

14.2. Endpoints

14.2.1. Primary endpoints

As this is a feasibility study in order to understand how the study can be done in a large cohort of pregnant women, a range of parameters (as detailed) will contribute to the feasibility objective.

14.2.2. Secondary endpoints

N/A

14.3. Sample size and recruitment

14.3.1. Sample size calculation

There is no formal sample size calculation as this is a pragmatic study conducted among a representative network of hospitals that is intended to assess the feasibility of approaching a much larger network of hospitals that is needed to achieve the main objective of this research. The proportions achieved against the various study endpoints will allow sample size calculations to be made for the main study.

In the feasibility study, the total number of livebirths represented at the 5 hospitals is approximately 7000 over the 4-month study period. We hope to recruit around 80% of eligible pregnant women during the study period, to collect cord blood in around 80% of women recruited and to capture key clinical data in 80% of recruited women. We would expect that approximately 15% of births will not be recruited leaving around 6600 eligible women. With this sample size we will be able to estimate a rate of 80% recruitment to within a 95% confidence interval of +/-1%, with similar confidence intervals for other estimates and for each individual hospital also (to assess relevance of hospital).

With regards to the swab study it is proposed to approach pregnant women in 2 hospitals only (St George's & Kingston Hospitals). Over the 4-month period there will be 3600 eligible women and thus a target of 1000 women implies a 28% recruitment rate that we believe is achievable. If 1000 participants are recruited we will continue to recruit until the end of the study period. Again the estimates of confidence intervals around these recruitment rates etc. will enable sample size calculations to be made for the main study.

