Collection of infant blood: *At Kingston and St George's Hospitals only*, and only in those women who are participating in both the delivery blood collection study and the colonisation study and who are shown to be colonised, they will also be invited to participate in the infant antibody kinetics sub-study. In this sub-study babies born to colonised mothers will be randomized to have one blood sample obtained, at 4, 8 or 12 weeks of age. This will be undertaken by suitably trained research nurses or doctors using venipuncture or capillary sampling (2 ml) and then blood will be processed and stored as described above.

Collection of Guthrie cards: *At Kingston and St George's Hospitals only*, and only in those women who are participating in both the delivery blood collection study and the colonisation study, they will also be invited to participate in the infant Guthrie card collection sub-study. In this sub-study mothers will be asked for permission to obtain a sample of the Guthrie card, which is obtained routinely in all babies at around 5 days of age. This will be obtained from the National Screening Laboratory and stored for antibody analysis.

iGBS surveillance: Microbiologists and paediatricians at the 5 participating hospitals will be engaged at the start of the study and information provided about the study and its rationale. They will be asked to make contact with study staff should a case of iGBS occur (only up to 5 cases would be expected with the cohort of this feasibility study). Study staff will additionally make contact with each laboratory on a weekly basis to ensure that cases have not been missed. When a case of iGBS occurs, the relevant paediatrician will be contacted by the study team and asked to recruit the mother and baby to the iGBS sub-study. Following consent from the mother, a sample of blood will be obtained from her and from her baby and processed as above. She will also be asked to provide a single rectovaginal swab to be processed as above.

Follow-up of babies: A follow-up telephone call will be made to all parents 90 days after their babies birth to establish whether the infants developed iGBS disease during this time period. This phone call will be made by a member of the study team.

Subsequent assessments

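### The ±1% precision claimed for each hospital holds only for the pooled cohort; the plan's own counts give about ±1.8 to 2.5% per hospital

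*Protocol*

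**What the plan says.** All the relevant statements are in protocol section 14.3.1 unless noted.

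- Source population: "the total number of livebirths represented at the 5 hospitals is approximately 7000 over the 4-month study period".
- Eligible women: "approximately 15% of births will not be recruited leaving around 6600 eligible women".
- Expected recruitment: "We hope to recruit around 80% of eligible pregnant women during the study period".
- Other main-cohort rates: "to collect cord blood in around 80% of women recruited and to capture key clinical data in 80% of recruited women".
- Precision: with that sample size, an 80% recruitment rate is to be estimated "to within a 95% confidence interval of +/-1" (in per cent), "with similar confidence intervals for other estimates and for each individual hospital also". A parenthesis adds that the hospital-level figure is meant to show whether the hospital matters.
- Swab study, in a separate paragraph and at two hospitals only: "Over the 4-month period there will be 3600 eligible women and thus a target of 1000 women implies a 28% recruitment rate". No half-width is given there.

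The synopsis (section 3) gives a target of about 4000 participants. The background (section 4) puts GBS colonisation in pregnancy at around 20%.

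**The concern.** A half-width for a proportion shrinks with the square root of the number of women. If the whole cohort just reaches ±1%, one of five hospitals cannot come close. The clause nevertheless says that it can, and gives a purpose for it: judging whether the hospital matters. The study is meant to inform a much larger network of hospitals, so variation between hospitals is one of its useful outputs. Anyone planning from this paragraph would believe that hospital rates will be known about twice as precisely as the design allows.

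**Working it through.** **Formula.** The 95% half-width of a proportion is h = 1.96 × √(p(1 − p)/n). At p = 0.80 this is h = 0.784/√n.

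**The plan's own figure.** With n = 6600, h = 0.784/81.24 = 0.97%. The stated ±1% reproduces.

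**Women needed for ±1% at 80%.** n = 0.16 × (1.96/0.01)² ≈ 6147, which is 93% of 6600. No single hospital among the five can supply that many.

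**Women per hospital.** Two hospitals have 3600 eligible women, on average 1800 each. The other three have 6600 − 3600 = 3000, on average 1000 each. The average over all five is 6600/5 = 1320. The protocol gives no count for any one hospital, so near-equal size within each group is an assumption.

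| Unit | n | Half-width at 80% | Ratio to pooled, √(6600/n) |
|---|---|---|---|
| Pooled cohort | 6600 | 0.97% | 1.0 |
| Each of the two larger hospitals | 1800 | 1.85% | 1.9 |
| Average hospital | 1320 | 2.16% | 2.2 |
| Each of the other three | 1000 | 2.48% | 2.6 |

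Wilson intervals give half-widths within about 0.1 point of these.

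**What holds without the equal-size assumption.** At least one of the two larger hospitals has 1800 women or fewer, so ±1.85% or wider. At least one of the other three has 1000 or fewer, so ±2.48% or wider. Even the two larger hospitals taken together give 0.784/√3600 = 1.3%, and the other three together give 0.784/√3000 = 1.4%.

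**Sensitivity to the eligible total.** Taking 15% off 7000 gives 5950, not 6600. The pooled half-width barely moves (0.784/√5950 = 1.02%). The other three hospitals would then average (5950 − 3600)/3 ≈ 783 women, with a half-width of 2.80%.

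**Other main-cohort rates.** Cord blood and key clinical data are each put at 80% of recruited women. With 0.8 × 6600 = 5280 recruited, h = 1.08%. With the synopsis target of 4000, h = 1.24%. Both are reasonably similar to ±1% when pooled. Within an average hospital they are 2.41% (0.8 × 1320 = 1056 recruited) or 2.77% (4000/5 = 800 recruited).

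**Sub-studies, for orientation.** Swab uptake of 1000/3600 = 27.8%: h = 1.96 × √(0.278 × 0.722/3600) = 1.46%. Colonisation of 20% in 1000: h = 1.96 × √(0.2 × 0.8/1000) = 2.48%.

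**The case against.** The strongest reply is that this is a feasibility study. Section 14.3.1 says there is no formal sample size calculation, and section 14.4.1 plans a descriptive analysis. A half-width near ±2.5 points is still useful for a feasibility rate, and the main study is to be sized from the proportions achieved. All of that stands, and it limits the weight of the point. It does not rescue the clause: a study need not state a precision, but one that it does state should be right.

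Three stronger readings are tempting and are not supported.

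- **That the claim for other estimates is also false.** The other rates named just before the clause are cord blood and clinical data, and for those the word similar is fair. The clause is tied to the main-cohort sample size. The swab study comes afterwards, with its own denominator and no half-width, so the protocol does not clearly promise ±1% for the sub-studies.
- **That rates based on iGBS cases would have no usable precision.** Section 10.3 does say that "only up to 5 cases would be expected with the cohort of this feasibility study". But section 5.2 lists consent to iGBS surveillance among the main-study operational rates, and Appendix 2 labels surveillance as for all participants. The documents do not say that this rate is measured among case families only.
- **That chance differences between hospitals would be reported as real.** Intervals computed from the observed data will have their true width whatever this sentence says, and no between-hospital test is planned. What is overstated is the planning precision.

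**Conclusion.** The hospital-level precision is wrong as written. ±1% is correct for an 80% rate in the pooled cohort of about 6600 and close to correct for the other pooled main-cohort rates. For single hospitals the plan's counts imply about ±1.8 to 2.5%, or nearer ±2.8% at the smaller hospitals if the eligible total is 5950. The exact hospital figures assume near-equal sizes within the group of two and the group of three; the finding that ±1% cannot be reached at any single hospital does not. This is an error in one planning statement. It does not undermine the study's design, its recruitment target or its eventual estimates.

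**What to change.** In section 14.3.1, limit ±1% to the pooled main-cohort rates. Replace the hospital clause with about ±1.8 to 2.5% per hospital, computed from each hospital's expected number of eligible women and with those numbers listed. Settle the eligible total (6600 or 5950) first, because the figures for the smaller hospitals depend on it.

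For clarity only, add that ±1% does not apply to the sub-studies, with examples: swab uptake of 28% among 3600 is about ±1.5%, and colonisation of 20% among 1000 is about ±2.5%.

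The cost is one reworded sentence and a less favourable stated precision. No sample, procedure or recruitment target changes.

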14.3.2. Planned recruitment rate

As this is a feasibility study, there are no planned recruitment rates, however, see above for estimates.

14.4. Statistical analysis plan

14.4.1. Summary of baseline data and flow of patients

A descriptive analysis will be undertaken. For example, the proportion of women approached who agree to participate in the blood collection study, the proportion of women who agree to participate from whom a blood sample is obtained, etc.

14.4.2. Primary endpoint analysis

As this is a feasibility study in order to understand how the study can be done in a large cohort of pregnant women, a range of parameters (as detailed) will contribute to the feasibility objective.

14.5. Secondary endpoint analysis

N/A

14.6. Sensitivity and other planned analyses (if applicable) $\ensuremath{\mathsf{N/A}}$

14.7. Interim analysis N/A

14.8. Other statistical considerations N/A

15. Committees in involved in the trial

15.1. Trial Steering Committee – To be assigned by the National Institute for Health Research.

16. Direct access to source data

The Investigator(s)/institution(s) will permit trial-related monitoring, audits, REC review, and regulatory inspection(s), providing direct access to source data/documents. Trial participants are informed of this during the informed consent discussion. The process will include participants being asked to consent to provide access to their medical notes.

17. Ethics and regulatory requirements

The site must conduct the trial in compliance with the protocol as agreed by the Sponsor and, which was given favourable opinion by the REC where applicable and the HRA approval.

The Chief Investigator will be provided (via the Sponsor) with file indexes E.G. JREODOC0003 Trial Master File (TMF) index and JREODOC0004 ISF index for use with SOP JREOSOP0019 'Preparation and Maintenance of the TMF' The CI will be responsible for the maintenance of the TMF and may delegate the responsibility of ISF maintenance to the PI at each participating site.

It is the responsibility of the PI at each site to ensure that all subsequent amendments gain the necessary approval. Refer to JREOSOP0011 'Management of Amendments'.

Within 90 days after the end of the trial, the CI and Sponsor will ensure that the REC is notified that the trial has finished. If the trial is terminated prematurely, those reports will be made within 15 days after the end of the trial. Refer to JREOSOP0015 'End of study declaration'

The CI will supply an End of Study report of the clinical trial to the REC within one year after the end of the trial. The sponsor can provide JREODOC0059 End of study Report template.

18. Finance

This study is funded by the National Institute for Health Research HTA 17/153/01.

19. Insurance and indemnity

St George's University Hospitals NHS Foundation Trust holds insurance to cover participants for injury caused by their participation in the clinical trial. Participants may be able to claim compensation if they can prove that St George's University Hospitals NHS Foundation Trust has been negligent. This includes negligence in the writing of the protocol, or selection of trial resources.

Where the Trial is conducted in a hospital, the local hospital has a duty of care to participants. St George's University Hospitals NHS Foundation Trust will not accept liability for any breach in the hospital's duty of care, or any negligence on the part of hospital employees. Hospitals selected to participate in this clinical trial shall provide clinical negligence insurance cover for harm caused by their employees and a copy of the relevant insurance policy or summary shall be provided to St George's University Hospitals NHS Foundation Trust, upon request.

Participants may be able to claim compensation for injury caused by participation in this Trial without the need to prove negligence on the part of St George's University Hospitals NHS Foundation Trust or another party.

If a participant indicates that they wish to make a claim for compensation, this needs to be brought to the attention of St George's University Hospitals NHS Foundation Trust immediately.

Failure to alert St George's University Hospitals NHS Foundation Trust without delay and to comply with requests for information by the sponsor or any designated Agents may lead to a lack of insurance cover for the incident.

NHS bodies are liable for clinical negligence and other negligent harm to individuals covered by their duty of care. NHS Institutions employing researchers are liable for negligent harm caused by the design of studies they initiate.

20. Intellectual and development policy

Unless otherwise specified in agreements, the following guidelines shall apply:

All Intellectual Property Rights and Know How (IP) related to the Protocol and the Trial are and shall remain the property of the Sponsor excluding:

1) Pre-existing IP related to clinical procedures of any Hospital.

2) Pre-existing IP related to analytical procedures of any external laboratory.

All contributors:

- shall assign their its rights in relation to all IP Rights and in all Know How, not excluded above to the Sponsor and at the request and expense of the Sponsor, shall execute all such documents and do all such other acts as the Sponsor may reasonably require in order to vest fully and effectively all such IP Rights and Know How in the Sponsor or its nominee.
- shall promptly disclose to the Sponsor any Know How generated pursuant to this Protocol and not excluded above and undertake to treat such Know How as confidential information jointly owned between it and the Sponsor.

Nothing in this section shall be construed so as to prevent or hinder any medical professional from using Know How gained during the performance of the Trial in the furtherance of its normal business activities, to the extent such use does not result in the disclosure or misuse of Confidential Information or the infringement of any IP Right of the Sponsor.

21. Publication policy

Publication: "Any activity that discloses, outside of the circle of trial investigators, any final or interim data or results of the Trial, or any details of the Trial methodology that have not been made public by the Sponsor including, for example, presentations at symposia, national or regional professional meetings, publications in journals, theses or dissertations."

All scientific contributors to the Trial have a responsibility to ensure that results of scientific interest arising from Trial are appropriately published and disseminated. The Sponsor has a firm commitment to publish the results of the Trial in a transparent and unbiased manner without consideration for commercial objectives.

To maximise the impact and scientific validity of the Trial, data shall be consolidated over the duration of the trial, reviewed internally among all investigators and not be submitted for publication prematurely. Lead in any publications arising from the Trial shall lie with the Sponsor in the first instance. The study will be registered on www.clinicaltrials.gov.

21.1. Before the official completion of the Trial,

All publications during this period are subject to permission by the Sponsor. If an investigator wishes to publish a sub-set of data without permission by the Sponsor during this period, the Steering Committee shall have the final say.

Exempt from this requirement are student theses that can be submitted for confidential evaluation but are subject to embargo for a period not shorter than the anticipated remaining duration of the trial.

21.2. Up to 180 days after the official completion of the Trial

During this period the Chief Investigator shall liaise with all investigators and strive to consolidate data and results and submit a manuscript for peer-review with a view to publication in a reputable academic journal or similar outlet as the Main Publication.

- The Chief Investigator shall be senior and corresponding author of the Main Publication.
- Insofar as compatible with the policies of the publication outlet and good academic practice, the other Investigators shall be listed in alphabetic order.
- Providers of analytical or technical services shall be acknowledged, but will only be listed as co-authors if their services were provided in a non-routine manner as part of a scientific collaboration.
- Members of the Steering Group shall only be acknowledged as co-authors if they contributed in other capacities as well.
- If there are disagreements about the substance, content, style, conclusions, or author list of the Main Publication, the Chief Investigator shall ask the Steering Group to arbitrate.

21.3. Beyond 180 days after the official completion of the Trial

After the Main Publication or after 180 days from Trial end date any Investigator or group of investigators may prepare further publications. In order to ensure that the Sponsor will be able to make comments and suggestions where pertinent, material for public dissemination will be submitted to the Sponsor for review at least sixty (60) days prior to submission for publication, public dissemination, or review by a publication committee. Sponsor's reasonable comments shall be reflected. All publications related to the Trial shall credit the Chief and Co-Investigators as co-authors where this would be in accordance with normal academic practice and shall acknowledge the Sponsor and the Funders.

22. Statement of Compliance

The trial will be conducted in compliance with the protocol, Sponsor's SOPs, GCP and the applicable regulatory requirement(s).

The study conduct shall comply with all relevant laws of the EU if directly applicable or of direct effect and all relevant laws and statutes of the UK country in which the study site is located including but not limited to, the Human Rights Act 1998, the Data Protection Act 1998, the Human Medicines Regulations 2012, the Medicines for Human Use (Clinical Trial) Regulations 2004, and with all relevant guidance relating to medicines and clinical studies from time to time in force including, but not limited to, the International Conference on the Harmonisation of Technical Requirements for the Registration of Pharmaceuticals for Human Use, the World Medical Association Declaration of Helsinki entitled 'Ethical Principles for Medical Research Involving Human Subjects' (2008 Version), the UK policy framework for Health and Social Care Research (Version 3.2, October 2017).

This study will be conducted in compliance with the protocol approved by the REC and according to GCP standards and UK Clinical Trials Regulation. No deviation from the protocol will be implemented without the prior review and approval of the Sponsor and REC except where it may be necessary to eliminate an immediate hazard to a research subject. In such a case, the deviation will be reported to the Sponsor and REC as soon as possible.

Sero-correlates against Group B Streptococcus Protocol V 2.0, 23/05/2018 R&D Protocol Code Number: 18.0089 Page 28 of 33

23. List of Protocol appendices

- Appendix 1 Summary of Protocol Revision History
